## **9.5. Study Size**

THAOS has been open since 2007. There is no set number of patients who will be enrolled in the survey. Patients will be enrolled from different countries around the world. All patients who take part in this survey will be followed until the survey is declared complete by Pfizer (currently estimated to be the year 2023) or as long as they are able to participate, or until they withdraw consent to participate.

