### **4 HYPOTHESES AND DECISION RULES**

There are no hypotheses associated with this survey. All analyses will be descriptive.

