## **8 STATISTICAL METHODOLOGY AND STATISTICAL ANALYSES**

### **8.1 STATISTICAL METHODS**

The key objectives of the survey are to better understand the natural history of ATTR (hereditary and wild-type forms) and the progression of disease in this patient population. Analysis of clinical outcomes will be conducted on all enrolled patients with available data. Outcomes will be examined separately for the untreated and tafamidis treated sets, as well as for appropriate subgroups within these set. Outcomes will include results of the key clinical, functional and QoL assessments used to define progression of disease.

Data will be summarized descriptively.

Continuous variables will be summarized using descriptive statistics ie, number of non-missing values and number of missing values [ie, n (missing)], mean, median, standard deviation (SD), minimum, maximum and 10th and 90th percentile.

Qualitative variables will be summarized by frequency counts and percentages. Unless otherwise specified, the calculation of proportions will be based on non-missing values.

In case the analysis refers only to certain visits, percentages will be based on the number of patients still present in the study at that visit, unless otherwise specified. Sample size in a subgroup needs to be at least 10 in order to have sufficient data to provide descriptive statistics, listings will be provided for smaller subgroups.

Kaplan-Meier estimates (product-limit estimates) will be presented including the median time with two-sided 95% confidence intervals (CIs), if the number of events are at least 5.

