### **8.2 STATISTICAL ANALYSES**

The baseline visit will be considered as the last available visit on or before the date of sign of informed consent form for the all-enrolled set and the untreated set (as well as any other subgroups corresponding to this untreated set). For the treated set (as well as any other subgroups corresponding to this treated set), the baseline will be considered as the last available value within 3 weeks prior to or 3 weeks after starting tafamidis.

For the subgroup of patients with off-label use, the baseline will be the last available value prior to receiving the first dose of tafamidis 80/61 mg.

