### Electrocardiogram

For ECG, the following summaries will be provided at baseline and by yearly intervals:

- Any abnormalities in rhythm (Y/N)
- Sinus pause (Y/N)
- Atrial flutter (Y/N)

- Atrial fibrillation (Y/N)
- Atrial premature beat (Y/N)
- Junctional rhythm (Y/N)
- Ventricular tachycardia (Y/N)
- Ventricular premature complexes (Y/N)
- Other rhythm abnormality (Y/N)
- Pacemaker with normal function (Y/N)
- Low voltage (Y/N)
- Conduction abnormalities(Y/N)
- Types of conduction abnormalities
- Morphology abnormalities
- Types of morphology abnormalities
- Pathologic Q-Waves observed
- Types of P-Q wave abnormalities
- ST Segment T Wave abnormalities
- Types of ST Segment abnormalities

Also for the following parameters corresponding to ECG, summary statistics for the baseline and change from baseline by yearly intervals will be provided:

- QRS Axis
- PR
- QRS
- QT
- QTc

The summaries will be done using the tafamidis untreated set with predominantly cardiac or mixed phenotype at enrollment, tafamidis treated set with predominantly cardiac or mixed phenotype at enrollment, CCI [REDACTED] and either predominantly cardiac or mixed phenotype at enrollment, tafamidis treated set for patients who switched from predominantly neurologic to mixed phenotype and tafamidis untreated set for patients who switched from predominantly neurologic to mixed phenotype.

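### QRS axis is an angle, but the SAP summarises it and its change from baseline linearly, with no recording scale or wrap rule, so any boundary crossing enters with an error of 360 degrees

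*SAP*

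**What the plan says.** SAP 8.2.6, Electrocardiogram, sets one rule for five measurements: QRS axis, PR, QRS, QT and QTc. It reads: "Also for the following parameters corresponding to ECG, summary statistics for the baseline and change from baseline by yearly intervals will be provided". The sets are the cardiac or mixed phenotype patients, treated and untreated, a partly blacked-out subset, and patients who moved from neurologic to mixed phenotype.

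That section does not name the statistics. SAP 8.1 does, for every continuous variable: "Continuous variables will be summarized using descriptive statistics ie, number of non-missing values and number of missing values", followed by "mean, median, standard deviation (SD), minimum, maximum" and the 10th and 90th percentiles. It also sets the smallest group to be summarised: "Sample size in a subgroup needs to be at least 10 in order to have sufficient data to provide descriptive statistics".

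SAP 8.2 says which baseline value is used (in the treated set, "the baseline will be considered as the last available value within 3 weeks prior to or 3 weeks after starting tafamidis") but not how a change in an angle is formed. The readable text gives QRS axis no unit, no recording range, no rule for bringing sites to one convention, no axis categories and no exception to the linear rule.

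**The concern.** PR, QRS, QT and QTc are time intervals, and subtraction and averaging suit them. QRS axis is a direction. On a -180 to +180 scale the break lies at 180 degrees; on a 0 to 359 scale it lies at 0. A small rotation across the break, taken as follow-up minus baseline, becomes nearly a full turn in the wrong direction.

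At stake is the reading of the yearly QRS axis rows. If crossings occur, the mean change can be displaced or change sign, and the SD and range can describe the scale rather than the patients. Small groups are the most exposed, because one patient then carries the most weight.

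**Working it through.** **Inputs from the documents.** The list of five parameters (SAP 8.2.6), the statistics and the minimum of 10 patients (SAP 8.1). No enrolment target exists (Protocol 9.5: "There is no set number of patients who will be enrolled in the survey"). The documents give no axis values, scale or stated result, so there is no planned figure to reproduce. Every distribution below is an assumption.

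**Step 1: one patient.** Let b be baseline and f follow-up.
- Raw change = f - b.
- Wrapped change = ((f - b + 180) mod 360) - 180.

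For +175 to -175: raw = -350; wrapped = (-170 mod 360) - 180 = 190 - 180 = +10. For 5 to 355 on a 0 to 359 scale: raw = +350; wrapped = (530 mod 360) - 180 = 170 - 180 = -10. The error is 360 degrees each time. For a rotation of under 180 degrees that does not cross the break, the two formulas agree.

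**Step 2: one crossing among n patients.** Shift in the mean = 360/n. With an assumed true SD of 15 degrees, SD is about sqrt(15² + 360² × (1/n)(1 - 1/n)).

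| n | shift in mean | approximate SD |
|---|---|---|
| 10 | 36 | sqrt(225 + 11664) = 109.0 |
| 50 | 7.2 | sqrt(225 + 2540.2) = 52.6 |
| 100 | 3.6 | sqrt(225 + 1283.0) = 38.8 |
| 500 | 0.72 | sqrt(225 + 258.7) = 22.0 |

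In the simplest case (n = 10, nine patients unchanged, one true rotation of +10 across the break), the raw mean is -350/10 = -35.0 and the correct mean is 10/10 = +1.0. The SDs are 110.7 and 3.2.

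**Step 3: how often crossings occur.** Assumed: true axis normal with mean between -60 and +60 and SD 40 or 60; true change normal with mean 0 and SD 15; 1,000,000 simulated pairs per scenario.

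| scale | pairs crossing | SD of change (true 15.0) | linear baseline mean |
|---|---|---|---|
| -180 to +180 | 0.002% to 1.2% | 15.1 to 39.5 | off by 0 to about 8 |
| 0 to 359 | 4.1% to 11.5% | 70 to 116 | a true 0 is reported as about 180 |

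**Step 4: a true drift.** Assumed: axis normal (-20, SD 40), change normal (-5, SD 15), with 0%, 5% or 15% of patients instead at an extreme axis (180, SD 30). On -180 to +180 the mean change is about -5, -4 and -2, with SD about 15, 34 and 54. On 0 to 359 the mean change is about +4 to +6, the wrong sign, with SD about 101 to 109, even with no extreme-axis patients. The median change is between -4.7 and -5.0 on the first scale and about -4 on the second.

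**Step 5: the axis level.** Two patients at +175 and -175 point almost the same way, but their linear mean is 0, the opposite direction. On 0 to 359, 350 and 10 average to 180 when the common direction is 0. With two values the median gives the same answer, so its resistance in Step 4 applies to the change, not to the level on a badly placed scale.

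**The case against.** The strongest reply is that the harm is conditional. If all sites record -180 to +180 and few patients have an extreme axis, the linear rule is almost exact: in Step 4 with no extreme-axis group, about 0.01% of pairs cross and the SD is about 15.5 against 15.0. No document supports 5% or 15% at an extreme axis, and none says that any site records 0 to 359. Data-entry detail is left to the Case Report Form Completion Guidelines, and Protocol 9.8.1 describes programmed checks on entry. Either could fix one scale, and blacked-out derivation text could hold more. This stands as a limit on size. Fixing a scale would still not define a wrapped change.

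The SAP also already plans the median and the 10th and 90th percentiles, so a plausible median beside a change near 350 would expose the artefact. This largely stands for the change. It is weakest at n = 10, where one crossing is already 10% of the group and reaches a 10th or 90th percentile.

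A reader might infer more: that the yearly ECG tables will be corrupted, that the method fails materially under either convention, that the SD and range mainly reflect wrap-around, or that ECG is one of few cardiac outcomes followed over time. The first three need a scale and an axis distribution that the documents do not give. The fourth cannot be checked, because several rows for the cardiac and mixed groups in SAP 8.2.8 are blacked out; the readable text also plans survival, hospitalisation, death and post-baseline symptoms by phenotype.

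**Conclusion.** The point holds as a specification gap. The SAP applies linear statistics and plain subtraction to an angle, without a scale or wrap rule. Each crossing puts a 360-degree error into that patient's change and shifts the mean by 360/n; this arithmetic rests on no assumption about the patients. Whether crossings will be rare or common is not established. Under the assumptions shown, the effect runs from negligible on a uniform -180 to +180 scale with few extreme axes to severe on 0 to 359; mixed site conventions would also be severe.

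The importance is minor. One of five ECG measurements is affected, and the SAP states: "There are no hypotheses associated with this survey. All analyses will be descriptive". ECG is not named among the safety endpoints in SAP 6.2, and no test or decision rule uses the axis.

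**What to change.** In SAP 8.2.6, move QRS axis out of the list it shares with PR, QRS, QT and QTc, and add:

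1. One stated recording scale, with all values converted to it before analysis.
2. Change from baseline as the shortest signed rotation, ((follow-up - baseline + 180) mod 360) - 180. The linear summaries in SAP 8.1 can then be applied to this change.
3. The axis level at baseline and each yearly interval summarised by circular mean and dispersion, or by axis categories, in place of a linear mean and SD.

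The cost is a short SAP addition, one line of code for the wrapped difference, and some programming for the level summary. Categories would need cut-offs, which the documents do not contain. A check of how sites recorded the axis is also needed. No new data are required, and every change that does not cross the boundary stays as it is, so nothing is lost if no crossing occurs.

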## 9.3. Variables

The objectives of THAOS are to describe the population of patients affected with ATTR amyloidosis and to enhance the understanding of the disease natural history, including the variability and progression of the hereditary and acquired forms of disease.

All visits are intended to be outpatient visits. Assessments are recommended but not required and will be determined by the investigator. All assessments that occur will be recorded in the THAOS electronic data record. The THAOS Electronic Case Report Form Completion Guidelines detail how the data for these assessments should be entered into the electronic data record. Blank worksheets and QoL questionnaires (available in patient’s native language) are available to download from the THAOS electronic data record.

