### 9.3.1. Study Assessments

- Written informed consent/assent.
- Inclusion/exclusion criteria.
- Patient demographics (year of birth, gender, ethnic origin, race (if allowed by local regulations)).
- TTR genetic test results.
- Family disease history (previous family history of ATTR amyloidosis).

- Medical history (past and current signs, symptoms, and medical diagnoses).
- Annual medical assessment (current signs and symptoms).
- General examination (weight/height, vital signs, CCI [REDACTED]).
- Concomitant medications (category, indication, start and stop dates).
- Hospitalizations (admission and discharge dates, reason for hospitalization).
- Transplant history and complications (date(s) of transplant(s), organ(s) transplanted, information on complications).
- AE/SAE reporting for tafamidis-treated subjects.
- Events of interest (as listed in Table 1, Summary of Safety Concerns to be Assessed in THAOS).
- Clinical laboratory data (hematology, clinical chemistry, liver function tests, thyroid function tests).
- Urinalysis (includes glomerular filtration rate [GFR]).
- Cardiovascular assessments (electrocardiogram, echocardiogram, Holter monitoring, CCI [REDACTED]).
- Neurologic assessments (deep tendon reflexes, sensation [pinprick, soft touch, vibration, and position sense], motor strength, nerve conduction studies).
- Eye examination (intraocular pressure, vitreous, presence of opacities).
- Body composition (total bone mineral density and content, total lean and fat mass).
- CCI [REDACTED]
- Patient death (data on patient death will be collected independently of the visit schedule).

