## 2.2 STUDY OBJECTIVES

The objectives of THAOS are to:

- Describe the population of patients affected with ATTR amyloidoses;
- Enhance the understanding of disease natural history, including the variability and progression of the hereditary and acquired forms of the disease;
- Better understand the genotype – phenotype relationship in ATTRv;
- Compare the progression of disease and overall survival in patients with ATTR amyloidosis with and without liver transplant;
- Foster an international community of medical experts who will develop recommendations on the clinical management of ATTR amyloidoses;
- Provide information to better understand the management and treatment of patients with ATTR amyloidoses through publication of the survey data;
- Provide information on off-label use of tafamidis by identifying patients who do not meet the inclusion criteria for transthyretin amyloid cardiomyopathy (ATTR-CM)
- For tafamidis-treated patients, collect and summarize all AE/SAE data, including for the specific safety concerns outlined in Table 1 Summary of Safety Concerns to be Assessed in THAOS comprising important identified risks, important potential risks, and missing information that includes long-term safety in ATTR-CM patients with **CCI** [REDACTED] Class IV.
- For patients not treated with tafamidis, collect and summarize additional data on the events of interest listed in Table 1.

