### **Echocardiogram**

For Echocardiogram, summary statistics for the baseline will be provided for:

- Left atrium
- Aortic root
- LV septum
- LV posterior wall

- LV diastolic diameter
- LV systolic diameter
- LV ejection
- RV free wall thickness
- Quantitative LV end systolic volumes
- Quantitative LV end diastolic volumes
- Transmitral E wave peak velocity
- E wave deceleration time
- Transmitral A wave Peak velocity
- Peak tricuspid regurgitation velocity
- Derived peak pulmonary artery systolic pressure
- Septal and Lateral Peak E, A, S
- Stroke volume
- Cardiac output

Also for the following parameters corresponding to Echocardiogram, summaries will be provided at baseline:

- Value abnormalities
- Types of value abnormalities
- Respiratory variation
- Sparkling

Echocardiogram summaries will be performed for the following sets: tafamidis untreated set with predominantly cardiac or mixed phenotype at enrollment, tafamidis treated set with predominantly cardiac or mixed phenotype at enrollment, CCI [REDACTED] and either predominantly cardiac or mixed phenotype at enrollment, tafamidis treated set for patients who switched from predominantly neurologic to mixed phenotype and tafamidis untreated set for patients who switched from predominantly neurologic to mixed phenotype.

*Note: For all the above safety events (Concomitant medications, hospitalization, AE/SAE, Deaths, Laboratory, Vitals and ECG) all events collected till last tafamidis dosing date +28 days will be summarized for the tafamidis treated set and its associated sub-sets.*

CCI [REDACTED]  
[REDACTED]  
[REDACTED]  
[REDACTED]  
[REDACTED]  
[REDACTED]

PFIZER CONFIDENTIAL

CCI [Redacted]

CCI [Redacted]

[Redacted]

[Redacted]

[Redacted]

[Redacted]

[Redacted]

[Redacted]

[Redacted]

[Redacted]

PFIZER CONFIDENTIAL

[Redacted]

CCI [Redacted]

[Redacted]

CCI [Redacted]

[Redacted]

- [Redacted]
- [Redacted]
- [Redacted]
- [Redacted]
- [Redacted]
- [Redacted]
- [Redacted]
- [Redacted]
- [Redacted]
- [Redacted]
- [Redacted]

[Redacted]

CCI [Redacted]

[Redacted]

[Redacted]

CCI [REDACTED]

[REDACTED]  
[REDACTED]  
[REDACTED]

[REDACTED]  
[REDACTED]

[REDACTED]

[REDACTED]  
[REDACTED]  
[REDACTED]

[REDACTED]

[REDACTED]  
[REDACTED]  
[REDACTED]

[REDACTED]

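### Yearly ECG summaries include neurologic patients only if they later become mixed, so emerging ECG abnormality in that group cannot be read free of selection

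*SAP*

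**What the plan says.** **ECG sets.** SAP 8.2.6, Electrocardiogram, plans rhythm, conduction, voltage and morphology findings at baseline and by year, plus yearly change from baseline in QRS axis, PR, QRS, QT and QTc. The sets are treated and untreated patients who are predominantly cardiac or mixed at enrollment, a partly redacted cardiac/mixed subset, the "tafamidis treated set for patients who switched from predominantly neurologic to mixed phenotype", and the same switchers in the untreated set.

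**Phenotype rules.** Under SAP 5.4 the predominantly neurologic phenotype requires that none of three cardiac criteria is present: rhythm disturbance on ECG, heart failure, dyspnea. The mixed phenotype in variant (ATTRv) disease requires at least one of them.

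**Pacing.** The ECG list includes the yes/no item "Pacemaker with normal function (Y/N" and an atrial fibrillation item. No legible text says how such tracings are handled in the interval summaries.

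**Echo.** The SAP states "For Echocardiogram, summary statistics for the baseline will be provided for" a list of measurements, with no follow-up summary. The SAP amendment log gives the reason that echo is collected only at baseline. Protocol 9.3.1 lists "Cardiovascular assessments (electrocardiogram, echocardiogram, Holter monitoring" without that limit, and Protocol 9.3 states "All assessments that occur will be recorded in the THAOS electronic data record".

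**The concern.** One stated objective is to "Enhance the understanding of disease natural history, including the variability and progression of the hereditary and acquired forms of the disease". For hereditary patients who enroll with neuropathy, the appearance of cardiac involvement is a central part of that progression. The only neurologic patients with yearly ECG output are those already known to have developed a cardiac criterion. A reader of the final report would see how often abnormalities occur in switchers, but not how often they occur among patients who started out neurologic.

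Two lesser matters affect the same outputs. A pacemaker fitted during follow-up can change QRS and QT for reasons other than the disease process being tracked, and PR has no clear meaning in atrial fibrillation. And a baseline echo in switchers cannot describe what changed around the switch.

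**Working it through.** There is no planned figure to reproduce. Protocol 9.5 says "There is no set number of patients who will be enrolled in the survey", and neither document gives a conversion rate, an ECG abnormality rate or a pacing rate. The check is therefore mainly a comparison of sections.

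**Step 1: who is in the yearly ECG tables.**

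| Phenotype at enrollment | Yearly ECG table in SAP 8.2.6 |
|---|---|
| Predominantly cardiac or mixed | Yes, treated and untreated |
| Predominantly neurologic, later mixed | Yes, as switchers only |
| Predominantly neurologic, never mixed | None legible |

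The column alignment of the grid in SAP 8.2.8 is not reliable in the available text, so this rests on the prose.

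**Step 2: how the switch overlaps the outcome.** A neurologic patient has none of the three cardiac criteria at the start and needs one to become mixed. One of them, rhythm disturbance, is also an ECG outcome in the table. The overlap is partial, because a switch can come through heart failure or dyspnea alone.

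**Step 3: what non-switchers may still show.** Low voltage, conduction abnormality, Q waves, PR and QRS are tabulated but are not switching criteria, so patients who never switch can change on them. SAP 5.4 also bars re-classification when the prior-visit measure is missing, so some new rhythm findings may never lead to a switch.

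**Step 4: small sets.** SAP 5.4 and 8.1 replace descriptive statistics with listings in subgroups below 10. The switchers are split into treated and untreated, which makes that more likely.

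**Step 5: illustrative size, all inputs assumed.** Let c be the share of baseline-neurologic patients who switch and q the share of switchers with an ECG rhythm abnormality. If every new rhythm abnormality triggers a switch, non-switchers have none, and prevalence in all neurologic patients is c × q.

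- c = 0.10, q = 0.30: switchers 30%, all 0.10 × 0.30 = 3%.
- c = 0.20, q = 0.60: switchers 60%, all 0.20 × 0.60 = 12%.
- c = 0.40, q = 0.90: switchers 90%, all 0.40 × 0.90 = 36%.

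The ratio is q / (c × q) = 1/c, that is 1/0.40 = 2.5 to 1/0.10 = 10.

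A version with assumed hazards agrees. Take 4% per year for rhythm abnormality and 6% per year for heart failure or dyspnea, over 5 years. Rhythm abnormality in all is 1 − exp(−0.04 × 5) = 0.181. Switching is 1 − exp(−0.10 × 5) = 0.393. Among switchers the share is 0.181 / 0.393 = 0.46, so 46% against 18%.

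For a given c, 1/c is an upper bound: rhythm abnormality in non-switchers would lower it. It does not apply to findings outside the switching rule.

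**Step 6: paced tracings.** SAP 8.1 describes continuous variables using non-missing values. With no special rule, a recorded interval from a paced tracing would enter by default. If a share p becomes paced after baseline and pacing changes QRS by d in each, the mean change moves by p × d. With p assumed at 5% to 20%, that is 5% to 20% of d. The documents give no value for d, so no figure in milliseconds is offered.

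**Step 7: echo.** The baseline-only summary agrees with the reason in the SAP log. That reason sits uneasily with the protocol's unrestricted listing and its recording rule. The cardiovascular rows of SAP Table 2 are not legible, so collection at return visits can be neither confirmed nor ruled out.

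**The case against.** The strongest reply is that the switcher table is labelled as such and that the SAP never uses it to estimate incidence: "There are no hypotheses associated with this survey. All analyses will be descriptive". Other outputs also cover neurologic patients. SAP 8.2.3 gives baseline abnormal ECG, heart failure, atrial fibrillation/flutter and pacemakers by phenotype. SAP 8.2.4 gives post-baseline symptoms by phenotype at enrollment. Hospitalizations, and adverse events in the treated set, are given by phenotype. The amendment log mentions phenotype shift tables, which could supply a conversion denominator. All of this narrows the gap. It does not close it: baseline ECG has no follow-up, symptoms are not tracings, and the current shift-table text is not legible.

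A reader might infer that the ECG and echo outputs cannot show cardiac progression at all. The documents do not support that. Patients cardiac or mixed at enrollment have yearly categorical findings and yearly interval change.

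A reader might also infer that the SAP pools paced tracings. It does not say so; only the absence of a legible rule is established. Simply excluding newly paced tracings is debatable, because it conditions on a later event and may remove the most progressed patients. The pacemaker item also does not by itself identify ventricular pacing on a tracing.

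Finally, a reader might infer that follow-up echo data exist and are being dropped. The protocol list is not a schedule, it contains one-time items, and assessments are recommended rather than required.

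**Conclusion.** The point holds for ECG in patients predominantly neurologic at enrollment. Their yearly ECG output is confined to a set chosen on a later event that partly overlaps the tabulated outcome, and no legible ECG table supplies the non-switchers. On the assumed inputs, rhythm abnormality among switchers is 2.5 to 10 times that among all neurologic patients. That range rests on 10% to 40% switching and on every rhythm abnormality triggering a switch. It describes how far a reader could be misled, not an error in a stated estimate.

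The pacing point is secondary: a missing handling rule of unknown size. The echo point is a discrepancy to reconcile, not a demonstrated loss of data. Redacted parts of the SAP may hold further cardiac outputs.

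**What to change.** 1. In SAP 8.2.6, run the ECG summaries on all patients predominantly neurologic at enrollment, treated and untreated, and keep switchers as a sub-column. SAP 8.2.4 already reports post-baseline symptoms by phenotype at enrollment with switchers as additional sets. The cost is SAP wording and extra table columns from existing data.
2. State how paced and atrial-fibrillation tracings enter the PR, QRS, QT and QTc change summaries. Show these with and without tracings flagged as paced, and PR also without atrial-fibrillation tracings, where the recorded items allow it. Report the share affected. The cost is a second set of interval rows, with fewer tracings in the restricted version.
3. Reconcile the baseline-only echo summary with Protocol 9.3 and 9.3.1. If follow-up values are in the database, summarise yearly echo change. If not, state that echo progression cannot be assessed. The cost is one database check, then either added tables or one sentence.
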